6.4 Study duration

One year.

7.0 ASSESSMENT OF EFFICACY

As this study is an immunological study, the following efficacy outcomes will be evaluated:

- Changes in peripheral blood cytokines within RMS patients between baseline and months 1 to 12 inclusive, for both groups. Luminex kit will be used.
- Changes on microbiome after FMT by analyzing the gut bacterial composition through stool analysis and blood bacteria DNA at baseline, and months 1 to 12 inclusive for both groups.
- Gut permeability through urine analysis at baseline, 6 and 12 months for both groups.

8.0 ASSESSMENT OF SAFETY

8.1 Head MRI

A contrast head MRI will be performed at baseline, 6 months and 12 months for both groups as a safety measure to evaluate any subclinical activity or any paradoxical effect potentially caused by the FMT.

8.2 Adverse events

8.2.1 Definition of an Adverse Event

An adverse event (AE) is defined as any undesirable physical, psychological, or behavioural event experienced by a subject in conjunction with their participation in the clinical trial, regardless of whether the event is procedure- or study product-related. This includes any condition (including a pre-existing condition) that was:

- Not present prior to study treatment initiation but appeared or reappeared following initiation of study treatment.
- Present prior to study treatment, but worsened during study treatment. (This could include any condition resulting from concurrent illness, reactions to concomitant medications, or progression of disease states).

The occurrence of an AE will be based on changes in the subject's physical examination, laboratory results, and/or signs and symptoms.

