Test product, dose and mode of administration, batch number to be provided by [name] lab at St. Joseph's Health Care, London, ON. For this study, fecal samples from healthy donors will be screened as per Health Canada guidelines. About 50-70g of the fecal sample is blended in 220ml saline in a Stomacher and filtered and transferred to an enema bag for transplantation. From here on this is known as "FMT" or "study medication".

Lot no. XXXXXX

Duration of treatment/study:

FMT rectal enema will be administered as scheduled per group, for up to 6 months.

Criteria for evaluation:

- Circulating cytokines levels (IL-1 β , IL-2, IL-4, IL-5, IL-6, IL-9, IL-10, IL-12p70, IL-13, IL-15, IL-17A, IL-17E/IL-25, IL-17F, IL-21, IL-22, IL-23, IL-27, IL-28A, IL-31, IL-33, GM-CSF, IFN γ , MIP-3 α , TNF α and TNF β).
- Gut microbiome through feces analysis
- Blood DNA bacteria
- Gut permeability through urine analysis
- All adverse events occurring during this study will be recorded. MS clinical functional status will be monitored using EDSS to assess any changes during the treatment period, as well as head MRI as a safety surrogate.

Statistical methods:

Adverse events will be coded using MedDRA dictionary. Incidence of adverse events by the severity, relationship to treatment, and outcome will be provided. Narratives of all serious adverse events and events causing death will be included. Laboratory parameters, vital signs and other safety parameters will be documented with the use of descriptive statistics.

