Patients will also undergo a contrast-enhanced brain MRI scan at Robarts Institute in London Ontario. Other baseline assessments (prior to the first dose of therapy) include an EDSS, pregnancy test (if applicable), and physical exam. Blood samples are also taken at this visit in order to establish a baseline for routine chemistry/hematology. After all this assessments FMT will be performed by a trained nurse via a rectal enema

Patients will return to the clinic for visit 4 weeks after the first FMT. Another stool sample to evaluate the microbial before the second FMT will be collected. Also peripheral blood samples for cytokines and blood bacterial DNA analysis. This same routine procedure will be

repeated at month 2, 3, 4 and 5 for the early intervention group and at month 6, 7, 8, 9, 10 and 11 for the late intervention group. Both groups will come to clinic at baseline and month 1 to 12 inclusive, even if they are not receiving FMT. During all visits, a stool sample, a cytokine sample and a blood DNA bacteria sample will be collected. It is worth mentioning that at 6 and 12 months another urine analysis will be done to evaluate gut permeability and MRI study at Robarts Institute, London, Ontario for safety assessment will be performed for both groups.

Another safety assessment in each visit after FMT is to review of any adverse events that may have occurred. All patients receiving at least 1 week of treatment will be eligible for analysis.

Table 1. Early Intervention Group Schedule

[figure not shown]
Study Months	Pre-Visit	Baseline	Month 1	Month 2	Month 3	Month 4	Month 5	Month 6	Month 7	Month 8	Month 9	Month 10	Month 11	Month 12
Visit Duration	1.5hours	1.5hours	1.5hours	1.5hours	1.5hours	1.5hours	1.5hours	45min	45min	45min	45min	45min	45min	45min
Informed Consent Form	X													
Fecal Transplantation		X	X	X	X	X	X							
Height		X												
Weight, Vital Signs		X	X	X	X	X	X	X	X	X	X	X	X	X
Stool Sample		X	X	X	X	X	X	X	X	X	X	X	X	X
Urine: Gut Permeability		X						X						X
Circulating Cytokine Levels and Blood DNA		X	X	X	X	X	X	X	X	X	X	X	X	X
MRI		X						X						X
Routine Hematology and Urinalysis		X	X	X	X	X	X	X	X	X	X	X	X	X
Physical Exam/ EDSS		X	X	X	X	X	X	X	X	X	X	X	X	X

Table 2. Late Intervention Group Schedule

Study Months	Pre-Visit	Baseline	Month 1	Month 2	Month 3	Month 4	Month 5	Month 6	Month 7	Month 8	Month 9	Month 10	Month 11	Month 12

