8.2.2 Reporting of an Adverse Event

All AEs regardless of causal relationship are to be recorded in the case report form (CRF) and other source documentation.

The Investigator must determine the intensity of any AEs according to a three-point scale: mild, moderate, severe, and reported on specific AE pages of the CRF. If the severity of an AE worsens during study drug administration, only the worst intensity should be reported on the AE page. If the AE lessens in intensity, no change in the severity is required.

Mild

Event may be noticeable to subject; does not influence daily activities; the AE resolves spontaneously or may require minimal therapeutic intervention;

Moderate

Event may make subject uncomfortable; performance of daily activities may be influenced; intervention may be needed; the AE produces no sequelae.

Severe

Event may cause noticeable discomfort; usually interferes with daily activities; subject may not be able to continue in the study; the AE produces sequelae, which require prolonged therapeutic intervention.

A mild, moderate or severe AE may or may not be serious. These terms are used to describe the intensity of a specific event (as in mild, moderate, or severe myocardial infarction). However, a severe event may be of relatively minor medical significance (such as severe headache) and is not necessarily serious. Seriousness rather than severity serves as a guide for defining regulatory reporting obligations.

The Investigator must also determine the causal relationship using the guidelines listed in Table 8.1 and Section 8.1.1. Life threatening AEs will be recorded as serious adverse events (SAEs) in the CRF and will be reported to the medical monitor.

All AEs will be followed until resolution. Resolution is defined as the disappearance of all signs or symptoms related to the adverse event or the stabilization of the adverse event with residual signs or symptoms that are not expected to improve.

Criteria for Determining Category of Relationship of Clinical Adverse Events to Treatment

Not related This category applies to those adverse events which, after careful consideration, are clearly and incontrovertibly due to extraneous causes (disease, environment, etc.)

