8.2.3 Definition of a Serious Adverse Event

Adverse events that are to be considered serious include the following:

- Death, regardless of cause, which occurs within 30 days of the last dose of study drug or if after 30 days is a result of delayed toxicity due to administration of the study drug.
- Immediately life-threatening AE
- Permanently disabling event.
- Hospitalization or prolonged hospitalization excluding those for protocol-specific procedures.
- Congenital anomaly.

“Life threatening” means that the study participant was, in the opinion of the Investigator, at immediate risk of death from the reaction as it occurred. Any other event thought by the Investigator to be serious should also be reported.

The term “severe” is used to grade intensity and is not synonymous with the term “serious”.

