9.4 Safety Analysis

Adverse events will be coded using MedDRA dictionary. Incidence of adverse events by the severity, relationship to treatment, and outcome will be provided. Narratives of all serious adverse events and events causing death will be included. Laboratory parameters, vital signs and other safety parameters will be documented with the use of descriptive statistics.

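### Adverse-event collection in the late group's months 0–6, the only FMT-naive concurrent randomised comparator for AEs, is not assured

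*Combined protocol and SAP*

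**What the plan says.** Three statements in the combined protocol and SAP point to study-wide capture of AEs:

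- Section 8.2.1 opens by defining an AE as any undesirable "event experienced by a subject in conjunction with their participation in the clinical trial, regardless of whether the event is procedure- or study product-related".
- The synopsis, under criteria for evaluation, states: "All adverse events occurring during this study will be recorded".
- Section 8.2.2 states: "All AEs regardless of causal relationship are to be recorded in the case report form (CRF) and other source documentation".

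The more specific text is tied to FMT:

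- The two conditions that 8.2.1 then lists are "Not present prior to study treatment initiation but appeared or reappeared following initiation of study treatment" and "Present prior to study treatment, but worsened during study treatment". The synopsis equates study medication with FMT, and the late group has none until month 6.
- Section 4 gives the only scheduled AE review: "Another safety assessment in each visit after FMT is to review of any adverse events that may have occurred".
- The evaluation lists in 6.2.1 and 6.2.2 name no AE enquiry. Section 6.2.2 allows an unscheduled visit once an event has occurred, but as an option. Tables 1 and 2 have no AE row.
- Section 8.2.3 lists as serious: "Death, regardless of cause, which occurs within 30 days of the last dose of study drug". A later death counts there only if it is due to delayed toxicity. Section 8.4 separately requires that any death during the study be reported.

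For analysis, Section 9.4 promises: "Incidence of adverse events by the severity, relationship to treatment, and outcome will be provided". It names neither randomised group nor FMT period. Section 9.7 limits all analyses and listings to patients who received one week of study treatment.

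**The concern.** Safety and tolerability are the secondary objectives in the synopsis, and Section 3.2 says that AEs are monitored to assess tolerability. The late group in months 0–6 is the only concurrent randomised group not yet exposed to FMT. The early group's months 6–12 run alongside the late group's FMT, but those patients have already been treated and may carry effects over.

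A general instruction to record all AEs does not say who is asked, or when. If the only scheduled question comes after FMT, treated patients are prompted every month and controls must volunteer their events. The trial is open label, so nothing offsets that difference. Under-recording in the control group makes FMT look worse than it is. Events not asked about at the time cannot be reliably recovered later.

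**Working it through.** The plan states no figure on this point, so there is none to reproduce. The check sets the texts side by side and then sizes what is exposed.

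**1. Who is asked, on the stated schedule.** Both groups attend at baseline and monthly to month 12 (Section 4). Early-group FMT runs from baseline to month 5, and late-group FMT from month 6 to month 11. Read literally, AE review after FMT applies to the early group at months 1–12 and to the late group at months 7–12. Over visits 1–6 that is 20 × 6 = 120 early-group patient-visits with review and none in the late group, whose month-6 assessments come before its first FMT.

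**2. Exposure at issue.** Inputs: 20 patients per group, 12 months of study, a 6-month control period.

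- Late-group control time: 20 × 6 = 120 patient-months.
- Whole study: 40 × 12 = 480 patient-months, so 120/480 = 25%.
- Randomised months 0–6: 40 × 6 = 240 patient-months, so 120/240 = 50%.

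**3. Direction of bias.** Suppose both groups have the same true AE rate, early-group events are all captured, and a fraction c of late-group events is captured. The observed rate ratio, FMT to control, is then 1/c. Any c below 1 shows an excess with FMT that does not exist.

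**4. Worst case, c = 0.** The late group shows 0/20. With 5 early-group patients affected, the two-sided Fisher exact p is 2 × C(20,5)/C(40,5) = 2 × 15,504/658,008 = 0.047. Five is the smallest such count with p ≤ 0.05. The chance of reaching it is P(X ≥ 5) for X ~ Binomial(20, r), where r is the common true 6-month risk:

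| Assumed r | Expected early-group patients with an AE | Chance of a spurious difference |
|---|---|---|
| 10% | 2.0 | 0.04 |
| 17.7% | 3.5 | 0.27 |
| 28.5% | 5.7 | 0.72 |
| 50% | 10.0 | 0.99 |

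All four risks are assumptions. The values 17.7% and 28.5% are borrowed from the systematic review of FMT safety described in Section 2.7. They are its incidence of FMT-attributable AEs by lower gastrointestinal routes and its total AE incidence. Neither is a 6-month risk in MS patients.

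**5. What the analysis would show.** Even with complete capture, 9.4 commits to no table separating randomised groups or treated from untreated time. Under 9.7, a late-group patient who leaves before month 6 has had no FMT and drops out of every listing, along with any control-period events.

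**6. Deaths.** The early group's last scheduled FMT is at month 5, so the 30-day window in 8.2.3 closes at about month 6. A late-group patient in months 0–6 has no last dose to count from. Section 8.4 has no such limit for deaths during the study. The two sections differ in wording.

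**The case against.** A reader might infer that the late group's control months lie outside the AE definition and must show zero events. The documents do not support that. The governing sentence of 8.2.1 refers to participation in the trial, and the two treatment-anchored conditions are introduced as included cases, not as a limit. The synopsis and 8.2.2 agree with that sentence. The c = 0 calculation is therefore a worst case and not what the protocol prescribes.

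A reader might also infer that deaths could go unreported. Section 8.4 requires any death during the study to be reported, the other seriousness criteria in 8.2.3 carry no dose window, and events the investigator considers serious are to be reported as well. What remains is a mismatch of wording.

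Nor are the control months the only source of randomised safety data. Physical examination, EDSS, vital signs and laboratory tests are scheduled monthly in both groups, and MRI at baseline, 6 and 12 months. Section 8.2.1 bases AE occurrence partly on examination and laboratory findings, so some control events would surface that way.

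The missing table row is weak evidence on its own. Tables 1 and 2 also omit concomitant medications and serum chemistry, which 6.2.1 and 6.2.2 require. But AE review, unlike those items, is missing from the visit lists too. Likewise, 9.4 does not prescribe a pooled table; it leaves the split unspecified.

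These points narrow the concern without removing it. None supplies a scheduled AE enquiry for the late group before its first FMT. Symptoms that leave no trace on examination or laboratory tests, such as the abdominal discomfort that Section 2.7 names as the commonest FMT-attributable event, depend on asking.

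**Conclusion.** The concern holds as a gap in assurance: the broad definition covers control-period events, but the stated schedule does not provide for asking about them. Followed as written, ascertainment is unequal over 120 patient-months, which is half of randomised months 0–6 and all of the FMT-naive concurrent control time. The bias runs against FMT. Its size depends on how many control events are volunteered or found on examination, which the documents do not allow one to estimate. The Fisher figure of 0.047 for 5/20 against 0/20 is an upper bound on the problem, resting on no control capture at all and equal true risks.

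Two further gaps add to it: no stated tabulation by group or FMT period in 9.4, and the exclusion in 9.7 of late-group patients who leave untreated. The death wording in 8.2.3 and 8.4 needs reconciling, but no deaths are shown to be lost. The change is worth making because it concerns a secondary objective and is cheap.

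**What to change.** 1. State one start point for AE and SAE collection, randomisation, running through month 12 in both groups. Reconcile the synopsis and Sections 4, 8.2.1, 8.2.2, 8.2.3 and 8.4 to it, including the two statements on death.
2. Schedule AE review, asked in the same way, at every monthly visit in both groups. Add it to Tables 1 and 2 and to the lists in 6.2.1 and 6.2.2.
3. In 9.4, tabulate AEs in months 0–6 by randomised group for all randomised patients, and give AE rates per patient-month for FMT and non-FMT periods. Amend 9.7 so that its one-week treatment requirement does not apply to these safety tables.

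Both groups already attend every month, so no visits are added. The cost is protocol wording, one row in each schedule table, and minor extra CRF and analysis work.

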8.2.2 Reporting of an Adverse Event

All AEs regardless of causal relationship are to be recorded in the case report form (CRF) and other source documentation.

The Investigator must determine the intensity of any AEs according to a three-point scale: mild, moderate, severe, and reported on specific AE pages of the CRF. If the severity of an AE worsens during study drug administration, only the worst intensity should be reported on the AE page. If the AE lessens in intensity, no change in the severity is required.

Mild

Event may be noticeable to subject; does not influence daily activities; the AE resolves spontaneously or may require minimal therapeutic intervention;

Moderate

Event may make subject uncomfortable; performance of daily activities may be influenced; intervention may be needed; the AE produces no sequelae.

Severe

Event may cause noticeable discomfort; usually interferes with daily activities; subject may not be able to continue in the study; the AE produces sequelae, which require prolonged therapeutic intervention.

A mild, moderate or severe AE may or may not be serious. These terms are used to describe the intensity of a specific event (as in mild, moderate, or severe myocardial infarction). However, a severe event may be of relatively minor medical significance (such as severe headache) and is not necessarily serious. Seriousness rather than severity serves as a guide for defining regulatory reporting obligations.

The Investigator must also determine the causal relationship using the guidelines listed in Table 8.1 and Section 8.1.1. Life threatening AEs will be recorded as serious adverse events (SAEs) in the CRF and will be reported to the medical monitor.

All AEs will be followed until resolution. Resolution is defined as the disappearance of all signs or symptoms related to the adverse event or the stabilization of the adverse event with residual signs or symptoms that are not expected to improve.

Criteria for Determining Category of Relationship of Clinical Adverse Events to Treatment

Not related This category applies to those adverse events which, after careful consideration, are clearly and incontrovertibly due to extraneous causes (disease, environment, etc.)

Unlikely (must have two) In general, this category can be considered applicable to those adverse events which, after careful medical consideration at the time they are evaluated, are judged to be unrelated to the test drug. An adverse event may be considered unlikely if or when:

- It does not follow a reasonable temporal sequence from administration of the test drug.
- It could readily have been produced by the subject's clinical state, environmental or toxic factors, or other modes of therapy administered to the subject.
- It does not follow a known pattern of response to the test drug.
- It does not reappear or worsen when the drug is re-administered.

Possibly (must have two) This category applies to those adverse events for which, after careful medical consideration at the time they are evaluated, a connection with the test drug administration appears unlikely but cannot be ruled out with certainty. An adverse event may be considered possibly related if or when:

- It follows a reasonable temporal sequence from administration of the test drug.
- It could not readily have been produced by the subject's clinical state, environmental or toxic factors, or other modes of therapy administered to the subject.
- It follows a known pattern of response to the test drug.

- Probably** (must have three) This category applies to those adverse events for which, after careful medical consideration at the time they are evaluated, are felt with a high degree of certainty to be related to the test drug. An adverse event may be considered probably related if or when:
- It follows a reasonable temporal sequence from administration of the test drug.
 - It could not be reasonably explained by the known characteristics of the subject's clinical state, environmental or toxic factors, or any other modes of therapy administered to the subject.
 - It disappears or decreases on cessation or reduction in dose. There are important exceptions when an adverse event does not disappear upon discontinuation of the drug, yet drug-relatedness clearly exists (e.g. bone marrow depression, fixed drug eruptions, tardive dyskinesia).
 - It follows a known pattern of response to the test drug.

- Definitely** (must have all) This category applies to those adverse events which, the Investigator feels are incontrovertibly related to test drug. An adverse event may be assigned an attribution of definitely related if or when:
- It follows a reasonable temporal sequence from administration of the test drug.
 - It could not be reasonably explained by the known characteristics of the subject's clinical state, environmental or toxic factors, or other modes of therapy administered to the subject.
 - It disappears or decreases on cessation or reduction in dose with re exposure to drug. (Note: this is not to be construed as requiring re-exposure of the subject; however, a category of definitely related can only be used when a recurrence is observed.)
 - It follows a known pattern of response to the test drug.

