2.7 Potential risks for FMT and study procedures

Two randomized control Trials (RCTs) reported mild adverse events attributed to FMT, including diarrhea, cramping, belching, nausea, abdominal pain, bloating, transient fever, and dizziness⁴¹. Serious adverse events were also described, including a case of Fournier gangrene⁶¹, but none were attributed to the FMT.

Eight case-series studies (reporting on 70 patients) did not explicitly mention harms; all others specifically commented on harms (or lack thereof). Possible procedure-related harms, including micro perforation with colonoscopy⁶² and gastrointestinal bleeding⁶³, peritonitis⁶⁴, and pneumonia⁶⁴ with use of the upper gastrointestinal tract route, were rarely reported. One case-series study reported on FMT use in 80 immuno compromised patients⁶⁵. Although serious adverse events (2 deaths and 10 hospitalizations) occurred in 12 patients (15%); 4 were considered related to FMT, and 5 were possibly related.

Because rare adverse events may be first reported as a case report, we examined case reports for such events. One report⁶⁶ described a patient with abdominal pain and hypotension 3 days after FMT by means of a gastro jejunostomy tube placed through an indwelling gastric tube. The patient had pneumoperitoneum, toxic megacolon, and polymicrobial bacteremia and subsequently died. Long-term data on harms were not reported.

According to published articles, transient adverse responses after FMT have been reported, including mild fever, abdominal pain, diarrhea, exhaust, flatulence, and fatigue. However, these adverse effects are self-limiting. De Leon et al⁶⁶ reported a UC patient quiescent for more than 20 years who developed a flare of UC after FMT. This case gives us cautionary information concerning FMT being used to treat CDI with UC. Moreover, a recent paper reported a UC patient who had a cytomegalovirus infection after performing home FMT without donor screening⁶⁷. As extracts of feces are mediators between the donor and recipient, FMT has the potential for transmitting occult infections even when strict donor screening is performed.

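### Section 8.2.2 separates Moderate from Severe by sequelae, an outcome, although the scale is meant to grade intensity, so the planned severity table could under-count severe events

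*Combined protocol and SAP*

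**What the plan says.** Section 8.2.2 sets a three-point scale.

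- **Mild** includes: "does not influence daily activities; the AE resolves spontaneously or may require minimal therapeutic intervention". It does not mention sequelae.
- **Moderate** covers discomfort and a possible influence on daily activities, and ends: "intervention may be needed; the AE produces no sequelae".
- **Severe** begins: "Event may cause noticeable discomfort; usually interferes with daily activities; subject may not be able to continue in the study". It ends: "the AE produces sequelae, which require prolonged therapeutic intervention".

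The text after the definitions states the purpose of the scale: "These terms are used to describe the intensity of a specific event". It then separates severity from seriousness and gives an example: "a severe event may be of relatively minor medical significance (such as severe headache) and is not necessarily serious". Section 8.2.3 repeats that severe is an intensity term. Section 8.2.2 also asks for the worst intensity when an event worsens.

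On use of the grade, section 9.4 says: "Incidence of adverse events by the severity, relationship to treatment, and outcome will be provided". Tolerability is a secondary objective in the synopsis, and section 3.2 assesses it through adverse events. On the transient reactions reported after FMT, section 2.7 says: "However, these adverse effects are self-limiting".

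**The concern.** An intensity scale should rank how bad an event was while it lasted. Here the firm boundary between the upper two grades is what the event left behind. The two can diverge, and they diverge most for the kind of reaction that section 2.7 leads one to expect after an enema: cramping, diarrhoea or fever that passes without residue.

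At stake is how the tolerability result reads. Section 9.4 plans narratives only for serious events and deaths. For an intense but non-serious reaction, the severity grade is therefore the main planned signal of how badly it was tolerated. The study is open label, so staff who know the treatment would be choosing between two conflicting instructions. Two investigators, each following section 8.2.2 in good faith, could grade the same event differently.

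**Working it through.** No figure in the documents depends on this wording, so there is nothing to reproduce. The check is to separate firm from hedged elements, apply them to test events, and compare the results with the intensity text.

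**Step 1. Firm and hedged elements.** In Severe, discomfort, interference with activities and inability to continue are each softened by *may* or *usually*. The sequelae element is not. In Moderate, discomfort, influence on activities and need for intervention are each softened by *may*. The absence of sequelae is not. Sequelae are thus the only unhedged line between the two grades. Mild has one firm exclusion: no influence on daily activities.

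**Step 2. Literal application to four events.**

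| Event | Mild | Moderate | Severe | Literal grade |
|---|---|---|---|---|
| A. Intense, disrupts activities, full recovery | fails (activities affected) | fits | fails (no sequelae) | Moderate |
| B. Affects activities, leaves sequelae not needing prolonged treatment | fails (activities affected) | fails (sequelae) | fails (no prolonged treatment) | none |
| C. Low intensity, activities unaffected, residual sign | can fit (silent on sequelae) | fails (sequelae) | fails unless prolonged treatment is needed | Mild |
| D. Intense, sequelae needing prolonged treatment | fails | fails | fits | Severe |

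Event A is displaced from Severe to Moderate. Event B has no grade. Event C is not a gap: Mild does not exclude residual signs, and the section's definition of resolution allows stabilisation with residual signs.

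**Step 3. Comparison with the intensity text.** If the grades describe intensity, events A and D should share a grade; under the definitions they do not. The section's own example, a severe headache of minor medical significance, is an event of type A if it clears without sequelae, so it does not meet the definition of Severe given just above it. Whether sequelae remain is also known only once an event has run its course, while the scale is meant to capture its worst intensity.

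**Step 4. Size.** Let *s* be the share of truly intense events that leave no sequelae.

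- Definitions followed strictly: at most 1 − *s* of those events stay in Severe, so at least *s* are lost.
- Intensity text followed: the loss is 0.

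The documents give no value for *s*. Over its whole range, *s* = 0 gives no loss from this source and *s* = 1 gives loss of the entire severe count. Nothing in the plan narrows this.

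**The case against.** The strongest reply is that a reader might infer that self-limiting reactions are barred from Severe, and that the documents do not say so. No rule requires every element of a grade to be met. Where the authors wanted such rules they wrote them: the causality categories in section 8.2.2 specify two, three or all criteria. The severity grades can be read as descriptive profiles, and the intensity statement, the headache example and section 8.2.3 all tell the investigator that an intense event may be called severe. This stands. The defect is an internal contradiction that leaves the grade to the reader, not a definite prohibition. It does not make the definitions harmless, because an investigator who follows them as written assigns a grade that contradicts the stated purpose.

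Three further limits also stand.

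- A reader might infer drift towards Mild. Mild requires that daily activities are unaffected, so a disruptive event can move only to Moderate.
- Section 2.7 describes the adverse events attributed to FMT in two randomised trials as mild. A low severe count could arise under any scale, and its absence could not be blamed on the wording alone.
- A reader might size the problem from the rate in section 2.7 for lower gastrointestinal routes: 76/430 = 17.7%, and 0.177 × 40 = 7.1 patients, if it carried over to MS. That counts patients with any FMT-attributable event, whatever its intensity. It is not a count of misgraded events.

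Finally, regulatory reporting follows seriousness, not severity. All adverse events are recorded, and serious ones receive narratives whatever their grade. No hypothesis test or stopping rule uses the severe count.

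**Conclusion.** The point holds as an inconsistency with a practical consequence. The Moderate and Severe definitions use sequelae as their only unhedged dividing line, against the same section's intensity statement and headache example and against section 8.2.3. Applied literally, they place an intense, fully resolving reaction in Moderate and leave one class of event ungraded. The severity table in section 9.4 could then under-count severe events.

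Whether it does depends on which text investigators follow. The loss runs from none to every intense event without sequelae, and the documents do not allow a narrower range. Bias in the table is a risk, not an established result. A report of no severe events could not be read with confidence while the two texts stand together. Capture and reporting of serious adverse events are unaffected.

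**What to change.** Reconcile the definitions with the intensity text:

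1. Delete the sequelae clause from Moderate and from Severe, including the prolonged-treatment condition attached to the latter.
2. Define all three grades by intensity and degree of interference with daily activities only.
3. Record sequelae under adverse event outcome. Section 9.4 already tabulates outcome, so no information is lost.

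The cost is two clauses of protocol wording and the matching CRF guidance, ideally settled before any events are graded. The one downside is that the severe count may look slightly less favourable. No other part of the safety analysis needs to change.
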